12.7.3. Interpretation of Definitions

AE Reporting Period

The study period during which AEs must be reported is normally defined as the time of consent to the end of the study treatment follow-up. However, for this study, the AE reporting period will be divided based on the three phases of the study.

- a. **Screening phase:** When all screening tests have been done, we will assess for any AEs related to the screening tests at the time of communication with the subject about whether he/she is officially eligible or ineligible for the study.

Preexisting Condition: A preexisting condition is one that is present at the start of the study. A preexisting condition should be recorded as an AE if the frequency, intensity, or the character of the condition worsens during the study period.

- b. **Waitlist phase:** We will only capture AEs that are pertinent to the study. Specifically the following will be captured:

1. Patient death,
2. Patient develops a condition that would exclude them from the study,
3. Patient is de-listed (taken off the heart transplant waitlist),
4. Patient is made inactive on the transplant waitlist,
5. Patient is transplanted with a non-HCV heart.

In order to ascertain these events, we will review the patient's medical record once a month, and will contact the patient (by phone, e-mail, or in-person) every 6-8 weeks.

- c. **Post-transplant phase:** All AEs will be assessed at every clinic visit when the subject is seen by a member of the study team.

- d. **Post-study:** At the last scheduled visit, the investigator will instruct each subject to report any subsequent event(s) that the subject, or the subject's personal physician, believes might reasonably be related to participation in this study.

All unresolved AEs considered possibly, probably or definitely related to the study drug should be followed by the investigator until the events are resolved, the subject is lost to follow-up, or the AE is otherwise explained. The investigator should notify the IRB of any death or AE occurring at any time after a subject has discontinued or terminated study participation that may reasonably be related to this study. The IRB will also be notified if the investigator should become aware of the development of cancer or of a congenital anomaly in a subsequently conceived offspring of a subject that has participated in this study.

General Physical Examination Findings (screening, post-transplant, and post-study phases)

At screening, any clinically significant abnormality should be recorded as a preexisting condition. At the end of the study, any new clinically significant findings/abnormalities that meet the definition of an AE must also be recorded and documented as an AE.

Abnormal Laboratory Values (post-transplant, and post-study phases)

A clinical laboratory abnormality should be documented as an AE if any one of the following conditions is met:

- The laboratory abnormality is considered clinically significant by the local PI and is not otherwise refuted by a repeat test to confirm the abnormality
- The abnormality suggests a disease and/or organ toxicity
- The abnormality is of a degree that requires active management; e.g. change of dose, discontinuation of the drug, more frequent follow-up assessments, further diagnostic investigation, etc.

Hospitalization, Prolonged Hospitalization or Surgery (post-transplant and post-study phase)

Any AE that results in hospitalization or prolonged hospitalization should be documented and reported as a serious AE unless specifically instructed otherwise in this protocol, with the exception of hospitalization at the time of a heart offer and/or heart transplant. Any condition responsible for surgery should be documented as an AE if the condition meets the criteria for an AE.

Neither the condition, hospitalization, prolonged hospitalization, nor surgery are reported as an AE in the following circumstances:

- Hospitalization or prolonged hospitalization for diagnostic or elective surgical procedures for a preexisting condition. Surgery should **not** be reported as an outcome of an AE if the purpose of the surgery was elective or diagnostic and the outcome was uneventful.
- Hospitalization or prolonged hospitalization for therapy of the target disease of the study, unless it is a worsening or increase in frequency of hospital admissions as judged by the clinical investigator.

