5.2. Specific aims

Primary aim:

1. Primary efficacy objective: To determine sustained virologic response (SVR) rates of open-label Zepatier in hepatitis C virus (HCV) negative patients who receive a heart transplant from a genotype 1 or 4 HCV-positive donor, leading to post-transplantation de-novo HCV infection.
2. Primary safety objective: To determine the safety of administration of open-label Zepatier among HCV-negative patients who receive a heart transplant from a genotype 1 or 4 HCV-positive donor and develop post-transplant HCV infection.

Secondary aim:

1. To determine 1-year graft survival rates of HCV-negative heart transplant patients who receive a heart transplant from a genotype 1 or 4 HCV-positive donor, including those who spontaneously clear HCV and those who receive open-label Zepatier upon development of de-novo HCV.
2. To obtain preliminary data on the distribution of changes in circulating biomarkers of endothelial damage and coronary vasculopathy in HCV-negative patients transplanted with hearts from HCV-positive donors prior to HCV treatment, after viral clearance, and after SVR.
3. To evaluate rates of spontaneous clearance of HCV among HCV-negative patients who receive a heart transplant from a genotype 1 or 4 HCV-positive donor.
4. To identify the viral reservoirs leading to HCV transmission in HCV-negative patients receiving a heart transplant from a HCV-positive donor based on endomyocardial biopsies, measures of HCV antigens in peripheral mononuclear blood cells, and histological examination of arterial and venous tissue surrounding the transplanted heart.
5. To compare the quality-of-life of HCV-negative patients receiving a heart transplant from a HCV-positive donor to those of similar patients remaining on the waitlist for a standard deceased donor heart transplant.

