10.6. Safety Analysis

All patients will be assessed for toxicity and included in the safety analysis. This analysis will include summaries of the incidence and grade of toxicities. Safety interim analyses will be performed at days 14, 30, 60, 90, 118, and 184, and will be reported at each DSMB meeting. SAEs will be evaluated by the DSMB..

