12.7. Safety and Adverse Events

12.7.1. Definitions

Adverse event (AE): Any untoward medical occurrence associated with the protocol procedures, whether or not considered product or process related. Any symptom, sign, illness or experience that develops or worsens in severity during the course of the study. Inter-current illnesses or injuries should be regarded as AEs. Abnormal results of diagnostic procedures are considered to be AEs if the abnormality:

- results in study withdrawal
- is associated with a serious AE
- is associated with clinical signs or symptoms
- leads to additional treatment or to further diagnostic tests
- is considered by the investigator to be of clinical significance

Serious adverse event (SAE): Adverse events are classified as serious or non-serious. A *serious adverse event* is any AE that is:

- fatal
- life-threatening
- requires or prolongs hospital stay
- results in persistent or significant disability or incapacity
- a congenital anomaly or birth defect
- an important medical event

Important medical events are those that may not be immediately life threatening, but are clearly of major clinical significance. They may jeopardize the subject, and may require intervention to prevent one of the other serious outcomes noted above. For example, drug overdose or abuse, a seizure that did not result in in-subject hospitalization or intensive treatment of bronchospasm in an emergency department would typically be considered serious.

All AEs that do not meet any of the criteria for serious should be regarded as *non-serious AEs*.

Suspected adverse reaction: Any adverse event for which there is a reasonable possibility that the drug/investigational product caused the adverse event. For reporting purposes, "reasonable possibility" means

there is evidence to suggest a causal relationship between the drug/investigational product and the adverse event.

Unanticipated Adverse Device Effect (ADE): is any serious adverse effect on health or safety, or any life-threatening problem or death caused by, or associated with, a device, if that effect, problem, or death was not previously identified in nature, severity, or degree of incidence in the investigational plan or application, or any other unanticipated serious problem associated with a device that relates to the rights, safety, or welfare of subjects.

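### The safety summary has no pre-dose baseline and no treatment-emergent rule, so it cannot separate events present before Zepatier from those arising or worsening on it

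*Combined protocol and SAP*

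**What the plan says.** - **Reference point.** Section 12.7.3 states: "A preexisting condition is one that is present at the start of the study". For examination findings it adds: "At screening, any clinically significant abnormality should be recorded as a preexisting condition". The closing comparison, made when follow-up finishes, looks for fresh findings: "any new clinically significant findings/abnormalities that meet the definition of an AE must also be recorded". No later section resets this reference. Section 10.2 mentions baseline safety measurements without giving a time point.
- **Definition of an AE.** Section 12.7.1 includes: "Any symptom, sign, illness or experience that develops or worsens in severity during the course of the study". The span is the whole study, not the time on drug.
- **Capture.** For the waitlist phase, section 12.7.3 says: "We will only capture AEs that are pertinent to the study", and lists five kinds of event. After transplant: "All AEs will be assessed at every clinic visit when the subject is seen by a member of the study team".
- **First dose.** Under section 8.1.3.3, Zepatier starts once HCV RNA is confirmed, at any time in weeks 1 to 4.
- **Analysis.** Sections 10.3 and 10.6 put all patients in the safety analysis. Section 10.6 says: "This analysis will include summaries of the incidence and grade of toxicities".
- **Objective.** The primary safety objective in section 5.2 is: "To determine the safety of administration of open-label Zepatier among HCV-negative patients who receive a heart transplant" and develop HCV infection. The synopsis lists major AEs attributable to HCV therapy as an endpoint. Section 9.2.1 covers AEs related to the HCV-positive heart as well as AEs related to Zepatier.
- **Relatedness.** The five-level scale in section 12.7.2 refers to the research procedures.

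**The concern.** The stated reference for what is already there is set before an open-ended wait, a heart transplant and new immunosuppression. Zepatier comes after all three. A finding that appears in between is not preexisting under section 12.7.3, can be recorded as an AE, and enters the same incidence and grade summary as an event that begins on the drug.

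What is at stake is the reading of the primary safety objective. In a single-arm trial of about 10 treated subjects there is no control group to show what transplantation alone produces. The timing of an event relative to first dose, and its grade relative to the pre-dose grade, are the main tools left for judging the drug, and the plan specifies neither.

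The same gap affects interim reports. Section 10.6 schedules safety analyses from day 14. The origin of that count is not stated. If it is the transplant, some subjects may not yet have been dosed at day 14, and the data monitoring board would receive one undivided summary.

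**Working it through.** The plan gives no figure on this point, so there is none to reproduce. The check sets the rules side by side and then gives a sense of scale.

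**1. What is recorded, by period**

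| Period | AE capture | Stated reference |
|---|---|---|
| Screening | AEs related to screening tests; preexisting conditions recorded | Start of study |
| Waitlist | Five listed event types | Start of study |
| Transplant to first dose (weeks 1 to 4) | All AEs at clinic visits | Not reset |
| On Zepatier | All AEs at clinic visits | Not reset |

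The analysis in sections 10.3 and 10.6 draws no line between the last two rows.

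**2. Three cases under these rules**

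- *Clinically significant examination finding first seen at Visit 1 (day 3 ± 1), before any dose.* It is not preexisting. If it meets the AE definition it is an AE and enters the summary. Nothing in section 10 marks it as pre-dose.
- *Abnormal laboratory value before first dose.* The laboratory rule in section 12.7.3 asks about clinical significance, suggested disease or organ toxicity, and need for active management. It compares with no earlier value, whether screening or pre-dose. Section 8.1.2 lists a hepatic panel at screening but no creatinine or blood count.
- *Abnormality present before first dose that worsens on Zepatier.* Recognising the worsening needs a pre-dose grade. None is designated.

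**3. Could the collected data separate the periods?** Largely, yes. AEs are assessed at Visit 1, section 12.7.2 requires a form entry for each AE, and section 12.7.4.1 lists onset and resolution dates among the details for event reports. But no rule says that the split will be made, and an onset date does not supply the reference grade for the third case.

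**4. Scale**

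Inputs: 10 treated subjects (synopsis and abstract); about 40% readmitted within 30 days of transplant (section 12.10.1). Under section 12.7.3 an AE leading to hospitalization is serious, apart from the transplant admission and the listed exceptions.

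- One treated subject: 1/10 = 10 percentage points.
- Expected readmitted within 30 days: 10 × 0.40 = 4.0.
- Probability of at least one: 1 − 0.6^10 = 0.994.

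The number readmitted before a first dose on day d depends on timing, which the documents do not give. Two assumptions are a uniform spread, 10 × 0.40 × d/30, and a constant hazard, 10 × (1 − 0.6^(d/30)):

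| First dose on day | Uniform | Constant hazard |
|---|---|---|
| 3 | 0.4 | 0.5 |
| 7 | 0.9 | 1.1 |
| 14 | 1.9 | 2.1 |
| 28 | 3.7 | 3.8 |

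The early rows are probably too high, because a patient still in hospital cannot be readmitted.

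**The case against.** The best defence is that the plan has an omission, not a wrong rule, and that the omission is easily repaired at analysis. Five parts of it deserve an answer.

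- **No on-treatment scoring.** A reader might infer that abnormalities present before Zepatier will be scored as new events on treatment, so that its toxicity is overstated. The documents do not say this. They define no on-treatment count at all. This stands.
- **Scope of the screening sentence.** A reader might also infer that creatinine, haemoglobin and liver enzymes are judged against screening. The screening sentence sits under examination findings, and the laboratory rule uses no baseline. This stands. It changes the mechanism for laboratory values but leaves them equally without a pre-dose reference.
- **One event, one onset.** An AE is something that develops or worsens. The text does not have a persisting abnormality counted again at each visit, so an analysis window defined by onset would remove most of the problem. This stands. The difficulty is that no such window is planned, and it would still need a reference grade for worsening.
- **Transplant events are wanted.** Section 9.2.1 deliberately includes AEs from receiving the HCV-positive heart. This stands, and those events should stay. It is a reason to tabulate them separately, not to pool them with drug events.
- **Drug attribution is foreseen.** The synopsis endpoint, the suspected-reaction definition in section 12.7.1 and the follow-up rule in section 12.7.3 all refer to the drug. This stands only in part, because the scale actually used to grade each event does not.

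**Conclusion.** The point holds as an omission. The only stated reference for preexisting conditions is the start of the study, and the safety analysis has no pre-dose baseline, no treatment-emergent definition and no split at first dose. Relatedness is not graded to Zepatier. Followed as written, the summary pools events from before the first dose with those arising or worsening on the drug, and so cannot by itself answer the primary safety objective.

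The size of any resulting distortion cannot be computed from the documents, which give no pre-dose rate of laboratory or examination abnormalities. What can be said is that each treated subject is worth 10 points when 10 are treated. The weight is smaller if the denominator is all patients, since subjects who clear HCV are replaced and the total may exceed 10. The readmission figures show only that events in the first month are likely. They rest on the protocol's 40% and an assumed timing, and not every readmission need be a serious AE.

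The direction is also open. Pooling could make Zepatier look worse than it is or hide a real effect among surgical events. This is a cheap improvement, not a flaw that invalidates the trial.

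**What to change.** In sections 12.7.3, 10.2 and 10.6:

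1. Keep capturing all AEs after transplant.
2. For treated subjects, define the safety baseline as the last available examination, vital signs, metabolic panel (CMP) and blood count (CBC) before the first Zepatier dose. Update the list of existing conditions at Visit 1.
3. Count an event as treatment-emergent only if its onset is after that dose, or if it is at least one CTCAE grade worse than that baseline.
4. Tabulate separately the events from transplant to first dose and the events in subjects who are never treated. Use the same split in the interim safety reports.
5. Record relatedness to Zepatier separately from relatedness to the HCV-positive transplant.

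The cost is protocol and analysis wording, a history entry at Visit 1, an added relatedness field and one more table. The schedule in section 8.2.1 already has CMP and CBC from day 3 through week 4 and an examination at Visit 1, so no test is added.

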1 SYNOPSIS

Title	Open-Labeled Trial Of Zepatier For Treatment Of Hepatitis C-Negative Patients Who Receive Heart Transplants From Hepatitis C-Positive Donors
Clinical study phase	II
Study objectives	
This study is being conducted to determine safety and efficacy of transplanting hearts from HCV virus (HCV)-positive donors into HCV-negative patients on the heart transplant waitlist, who will then be treated with Zepatier status post-single heart transplantation.
 
Primary aim:
 
 1. Primary efficacy objective: to determine sustained virologic response (SVR) rates of open-label Zepatier in HCV-negative patients who receive a heart transplant from a genotype 1 or 4 HCV-positive donor, leading to post-transplantation de-novo HCV infection. 2. Primary safety objective: to determine the safety of administration of open-label Zepatier among HCV-negative patients who receive a heart transplant from a genotype 1 or 4 HCV-positive donor and develop post-transplant HCV infection. 
Secondary aims:
 
 3. To determine 1-year graft survival rates of HCV-negative heart transplant patients who receive a heart transplant from a genotype 1 or 4 HCV-positive donor, including those who spontaneously clear HCV (and those who receive open-label Zepatier upon development of de-novo HCV). 4. To evaluate rates of spontaneous clearance of HCV among HCV-negative patients who receive a single heart transplant from a genotype 1 HCV-positive donor.
Indication	Chronic HCV post-heart transplantation
Diagnosis and main criteria for inclusion	
Inclusion criteria
 
 • New York Heart Association (NYHA) Class III or IV CHF refractory to maximal medical therapy (ACE inhibitor, B-blocker, digoxin and diuretics, resynchronization therapy or ICD when applicable) and/or conventional surgery AND/OR Inoperable coronary artery disease with intractable anginal symptoms AND/OR Malignant ventricular arrhythmias unresponsive to medical or surgical therapy • 40-65 years of age • Obtained agreement for participation from the transplant cardiology team • No evident contraindication to liver transplantation other than the underlying cardiac disorder • Able to travel to the University of Pennsylvania for routine post-transplant visits and study visits for a minimum of 6 months after transplantation

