9.2.1. Safety

Subject safety and adverse events will be based in CTCAE Version 4 criteria, listed in Section 13, and will include adverse events and serious adverse events, related both to receipt of a heart transplant from an HCV-positive donor among HCV-negative subjects with heart failure, and adverse events related to administration of Zepatier.

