12.10.5. Risks of Developing HCV

The risks of chronic HCV include severe acute inflammation of the liver that could lead to liver failure requiring a liver transplant. HCV may also cause a severe type of acute infection called fibrosing cholestatic HCV, that can cause severe liver injury, jaundice (yellowing of the eyes and skin), and progressive liver dysfunction.

There is a small risk of transmission of HCV from the study subject to intimate partners during sexual activity. This risk is very low and should be reduced even further due to requirements for subjects to use barrier protection during sexual activity.

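### Section 12.7.3 exempts admissions for an undefined target disease from AE reporting, so admissions for the donor-derived HCV infection can go unreported at an unblinded investigator's discretion, contrary to 9.2.1 and 12.7.1

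*Combined protocol and SAP*

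**What the plan says.** The hospitalization paragraph of 12.7.3 applies to the post-transplant and post-study phases. It opens with a default: "Any AE that results in hospitalization or prolonged hospitalization should be documented and reported as a serious AE unless specifically instructed otherwise in this protocol". The admission for the heart offer or the transplant itself is excepted there.

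The paragraph then introduces a list with "Neither the condition, hospitalization, prolonged hospitalization, nor surgery are reported as an AE in the following circumstances". The second item is "Hospitalization or prolonged hospitalization for therapy of the target disease of the study", qualified by "unless it is a worsening or increase in frequency of hospital admissions as judged by the clinical investigator".

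The documents do not define the target disease. The nearest statement is the Indication row of the Synopsis: "Chronic HCV post-heart transplantation".

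Section 9.2.1 says the safety outcome will include AEs and SAEs "related both to receipt of a heart transplant from an HCV-positive donor among HCV-negative subjects with heart failure", as well as those related to Zepatier. Section 12.7.1 treats any illness that arises or worsens during the study as an AE, and any AE that leads to or lengthens a hospital stay as serious. Section 12.10.5 warns that "HCV may also cause a severe type of acute infection called fibrosing cholestatic HCV" and names liver failure among the risks.

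Safety is a primary objective in the Synopsis and in 5.2 ("Primary safety objective: To determine the safety of administration of open-label Zepatier among HCV-negative patients"). It is listed as a secondary endpoint in the Synopsis analysis plan and as a secondary outcome in 9.2.

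**The concern.** An exemption of this kind suits a trial whose subjects bring the disease with them, where admissions for it are background. Here the position is reversed. Section 6.2.2 excludes anyone positive for HCV antibody or RNA, so the infection always begins on study and comes from the study procedure. An exemption for treating it would leave out a harm that the trial exists to measure.

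The item removes the condition as well as the admission. An event that is never classified as an AE or SAE can miss the incidence and grade summaries in 10.3 and 10.6, the data safety monitoring board (DSMB) review in 10.6 and 11.2, and the forwarding of SAEs to the manufacturer in 12.7.4.1. The only way back is a judgement for which the protocol gives no criteria, made by investigators who know the treatment and the donor's status. Any error would be towards too few events.

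**Working it through.** The plan gives no figure on this point, so there is none to reproduce. The check is mainly a comparison of the text.

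**1. Does the exemption override the SAE default?** Yes. The default in 12.7.3 yields to any contrary instruction in the protocol, and the list that follows is such an instruction.

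**2. What is the target disease?** It is undefined, and there are two candidates.
- *HCV infection.* It is the Synopsis indication and the disease the study drug treats, and it exists in the phases to which the paragraph applies. This is the natural reading, but it is an inference.
- *The underlying heart disease.* It is the reason for transplant. On this reading the item might be applied to admissions for a failing graft. That is less clear, because 12.10.1 lists graft non-function and rejection as risks of the transplant rather than as the original disease.

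**3. Does the exemption agree with the other sections?** Take an admission to treat hepatitis caused by the donor's virus.

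| Section | Treatment of the event |
|---|---|
| 12.7.1 | AE (arose on study); SAE (required a hospital stay) |
| 9.2.1 | Included, as related to receipt of the HCV-positive heart |
| 12.7.3, exemption | Neither condition nor admission reported, unless the investigator invokes the qualifier |

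The three sections cannot all be followed unless the qualifier is invoked every time.

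**4. Does the qualifier settle it?** It asks for a worsening or an increase in admissions. All subjects start without HCV, so the text does not say against what a first admission is to be compared.

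**5. Scale, for illustration only.** Input: n = 10 planned subjects (Synopsis). Exact (Clopper-Pearson) 95% limits:
- 0/10: upper limit = 1 − 0.025^(1/10) = 0.3085, so 0% to 30.8%.
- 1/10: lower limit = 1 − 0.975^(1/10) = 0.0025; upper limit = 97.5th percentile of Beta(2, 9) = 0.445, so 0.3% to 44.5%.

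One unreported admission moves the estimate from 10% to 0% and the upper limit from 44.5% to 30.8%.

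The documents give no HCV-admission risk p. With p assumed, the chance of at least one such admission among 10 is 1 − (1 − p)^10:
- p = 5%: 1 − 0.95^10 = 40%
- p = 10%: 1 − 0.90^10 = 65%
- p = 20%: 1 − 0.80^10 = 89%

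These values show only how the chance depends on the assumption.

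**The case against.** **The qualifier may restore the events.** Admissions for HCV before the study are zero by design, so a first one could be called an increase, and new hepatitis a worsening. This is a fair reading, and it is why the loss is not automatic. But the text does not require it, and two investigators could decide differently on the same case.

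**The exempted act is narrow.** HCV therapy here is a daily tablet, and 7.1.1 expects patients to be at home when it starts. The indication is chronic HCV, whereas the feared complications are acute. The first part limits how often the item would apply. The second carries less weight, because 12.10.5 itself lists severe acute liver inflammation and liver failure among the risks of chronic HCV.

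**Other rules keep part of the information.** Under 12.7.3 a laboratory abnormality that points to organ toxicity is an AE in its own right, and AEs are assessed at every post-transplant clinic visit. Death and re-transplantation count as graft failure under 9.2.2. These safeguards are real but partial: the laboratory rule does not make the admission an SAE, and graft failure misses a non-fatal hepatitis admission. The provision in 12.7.4.1 for rare events such as hepatic necrosis applies to unexpected SAEs, so the event must first be classified as one.

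**The specific statement in 9.2.1 should guide the general item.** That is a sensible way to resolve the conflict, but staff completing AE forms will follow the reporting rule.

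**The safety analysis is descriptive.** No test or threshold is affected. The counts themselves are still the result, so a missing event matters.

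**Conclusion.** The point holds as a contradiction between the reporting rule in 12.7.3 and both 9.2.1 and 12.7.1. It permits under-reporting of admissions for an infection that the study causes. It rests on reading the target disease as the Synopsis indication, which is a sound inference but not a definition in the protocol.

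A reader might infer more than the documents support:
- *That HCV admissions will be lost.* The qualifier makes this a matter of discretion.
- *That several admissions would be affected, because 12.10.1 expects about 40% of patients to be readmitted within 30 days.* That figure gives no cause and says nothing about HCV admissions.
- *That each event is worth exactly 10 percentage points.* Section 10.6 includes all patients in the safety analysis, and subjects who clear the virus spontaneously are replaced (8.1.3.6), so the denominator may exceed 10 and each event would then weigh less.
- *That a primary endpoint is compromised.* Safety is a primary objective, but it is listed as a secondary endpoint.

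The change should be made: the events concerned are few but central, and the correction is simple.

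**What to change.** Delete the target-disease item from the list in 12.7.3. Nothing needed is lost, because the index transplant admission is already excepted earlier in the same paragraph.

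Alternatively, keep the item, define the target disease, and add a sentence such as: *This exemption does not apply to post-transplant admissions for HCV infection or its complications, or for events related to the transplanted heart; these are recorded as AEs or SAEs and included in the safety analysis.* Either change brings 12.7.3 into line with 9.2.1 and 12.7.1.

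The cost is a short protocol edit, a few more SAE forms and possibly a higher reported SAE rate. No treatment or visit changes.
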